8.4.3 REPORTING UNANTICIPATED PROBLEMS TO PARTICIPANTS

AEs will be reported to participants if they are unexpected, related or possibly related, and suggest greater risk of harm to participants.

9 STATISTICAL CONSIDERATIONS

9.1 STATISTICAL HYPOTHESES

- Primary Efficacy Endpoint(s): That one of the doses of vitamin E at 133.4 mg (200 IU), 266.8 mg (400 IU), or 533.6 mg (800 IU) daily is the minimum effective dose for improving relative change in alanine aminotransferase (ALT) from baseline to 24 weeks.
- Secondary Efficacy Endpoints(s): That one or more of vitamin E at 133.4 mg (200 IU), 266.8 mg (400 IU), or 533.6 mg (800 IU) daily is better than placebo in improving:
 - Proportion of patients achieving normalization* of ALT at 24 weeks
 - Mean change in ALT from baseline to 24 weeks
 - Mean change in AST and GGT from baseline to 24 weeks
 - Mean change in hepatic fat determined by FibroScan® CAP score from baseline to 24 weeks
 - Mean change in liver stiffness as assessed by FibroScan® from baseline to 24 weeks
 - Time course and end of treatment improvement in ALT, AST, GGT, and alkaline phosphatase
 - Time course and end of treatment improvement in C-reactive protein (serum marker of inflammation)
 - Time course and end of treatment improvement in change in total cholesterol, LDL cholesterol, HDL cholesterol, and serum triglycerides
 - Changes in fasting glucose levels from baseline to 24 weeks
 - Change in anthropometric measurements (weight, BMI, waist to hip ratio, waist circumference) from baseline to 24 weeks
 - Change in symptom assessment scores from baseline to 24 weeks
 - Change in frequency of CTCAE defined adverse events from baseline to 24 weeks
 - Mean change in ALT from 24 to 48 weeks (post-treatment).

- Mean change in AST and GGT from 24 to 48 weeks (post-treatment).
- Mean change in hepatic fat determined by FibroScan® CAP score from 24 to 48 weeks (post-treatment).
- Mean change in liver stiffness as assessed by FibroScan® from 24 to 48 weeks (post-treatment).

*Normalization of ALT is defined as a decrease in ALT to less than or equal to the ULN at the 24 week visit among participants who had an ALT value greater than ULN at baseline. Values for ULN are defined at each clinical center per institutional guidelines.

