1.2 SCHEMA

1.3 DATA COLLECTION SCHEDULE (DCS)

Assessment/Procedure	Screening Visits		Follow-up visits Weeks from Randomization						
	S	RZ	F04	F08	F12	F24	F28	F36	F48
Consent and reaffirmation	X	X
Baseline medical history	X
Follow-up medical history (with AUDIT-C)	.	.	X	X	X	X	X	X	X
Alcohol Use Disorders Identification Test (AUDIT)	X
Lifetime Drinking History (Skinner)	X
Review for adverse effects	.	.	X	X	X	X	X	X	X
Review for concomitant medications	X	X	X	X	X	X	X	X	X
Drug dispensing	.	X
Review of study drug adherence	.	.	X	X	X	X	.	.	.
Detailed* (D) or Focused† (F) physical exam	D	.	F	F	D	D	F	F	D
NASH CRN Liver Symptom Questionnaire	X	.	X	X	X	X	X	X	X
Cardiovascular risk factor assessment	X	X	.	.	X
Beverage Intake Questionnaire (BEVQ-15)	X	X	.	.	X
FibroScan®: liver stiffness and steatosis (CAP)	X	X	.	.	X
Complete blood count (CBC) ‡	X	X	.	.	X
Basic metabolic panel (BMP) §	X	X	.	.	X
Fasting lipid profile¶	X	.	.	.	X	X	.	.	X
Hepatic panel** and GGT	X	.	X	X	X	X	X	X	X
Fasting glucose and insulin	X	.	X	X	X	X	X	X	X
Prothrombin time (PT), activated Partial Thromboplastin Time (aPTT), and INR	X	X	.	.	X
HbA1c	X	X	.	.	X
C-reactive protein (CRP)	X	.	.	.	X	X	.	.	X
Pregnancy test	X	X	.	.	.
Prostate Specific Antigen (PSA) Test††	X	X
Banking‡‡: Fasting serum, plasma	X	.	.	.	X	X	.	.	X
Etiologic tests§§	X
Closeout form	X

* **Detailed physical exam:** anthropometric assessments (body weight [kg], body height [cm], waist circumference [cm], and hip circumference [cm]); vital signs (temperature, heart rate, respiratory rate, blood pressure), organ systems (skin, chest, lungs, heart, abdomen, nervous); liver signs and changes in bleeding (e.g. bleeding gums).

† **Focused physical exam:** anthropometric assessments (body weight [kg], body height [cm], waist circumference [cm], and hip circumference [cm]); vital signs (temperature, heart rate, respiratory rate, blood pressure); liver signs and **changes in bleeding (e.g. bleeding gums)**. The focused physical exam may be completed remotely via telemedicine video call per institutional guidelines.

‡ **Complete blood count:** hemoglobin, hematocrit, mean corpuscular volume (MCV), white blood cell count (WBC), red blood cell count (RBC), platelet count

§ **Basic metabolic panel:** glucose, calcium, sodium, potassium, CO₂ (carbon dioxide, bicarbonate), chloride, blood urea nitrogen (BUN), creatinine. eGFR will be calculated using the CKD-EPI formula.

¶ **Fasting Lipid profile:** total cholesterol, triglyceride, LDL, HDL.

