8.1.3 RANDOMIZATION

The randomization visit is the visit at which randomization takes place and the patient is issued the study medication randomly assigned to the patient. Randomization is the act of generating the random study medication assignment and is the procedure which defines a patient's enrollment into the trial. Randomization can only occur after eligibility has been fully checked and all data collected at the screening visits have been keyed to the trial database. Since these processes take time, randomization cannot be done at a screening visit, and since study medication needs to be issued to the patient, the randomization visit must be completed in person with the patient. Therefore, a visit separate from the screening visit is necessary. Since this will be a visit on a different calendar day and the study medication will be prescribed at this visit, good clinical practice requires that a few basic checks of the patient's well-being be completed at the randomization visit.

The procedures completed at the randomization visit are: verification that the patient is feeling well; affirmation of consent; review of concomitant drugs and vital signs (systolic and diastolic blood pressure, heart rate, respiratory rate, body temperature). All patients will be given information on a healthy life style and diet appropriate for their weight and other factors.

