8.3.4 TIME PERIOD AND FREQUENCY FOR EVENT ASSESSMENT AND FOLLOW-UP

The occurrence of an adverse event (AE) or serious adverse event (SAE) may come to the attention of study personnel during study visits and interviews of a study participant presenting for medical care, or upon review by a study monitor.

All AEs including local and systemic reactions not meeting the criteria for SAEs will be captured on the appropriate case report form (CRF). Information to be collected includes event description, time of onset, clinician's assessment of severity, relationship to study product (assessed only by those with the training and authority to make a diagnosis), and time of resolution/stabilization of the event. All AEs occurring while on study must be documented appropriately regardless of relationship. All AEs will be followed to adequate resolution.

Any medical condition that is present at the time that the participant is screened will be considered as baseline and not reported as an AE. However, if the study participant's condition deteriorates at any time during the study, it will be recorded as an AE.

Changes in the severity of an AE will be documented to allow an assessment of the duration of the event at each level of severity to be performed. AEs characterized as intermittent require documentation of onset and duration of each episode.

Site coordinators will record all reportable events with start dates occurring any time after informed consent is obtained until 7 (for non-serious AEs) or 30 days (for SAEs) after the last day of study participation. At each study visit, the investigator will inquire about the occurrence of AE/SAEs since the last visit. Events will be followed for outcome information until resolution or stabilization.

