9.4.3 ANALYSIS OF THE SECONDARY ENDPOINT(S)

For each secondary endpoint:

- Analyses of secondary endpoints are not dependent on findings of the primary endpoint or on the results of the Williams' test performed on the primary endpoint.
- Analyses will use complete case subjects of the Intention-to-Treat (ITT) Analysis Dataset (i.e., all randomized participants with complete data on each specific secondary endpoint).

The analysis of the 16 secondary endpoints listed in Section 3, Objectives and Endpoints, endpoints will use ANCOVA for continuous endpoints, logistic regression for binary endpoints, and Poisson regression for counts. Complete case analyses will be used for each secondary endpoint, if missing data on that endpoint < 10% and multiple imputation will be used if missing data on the secondary endpoint is 10% or greater. The covariate in the continuous endpoint ANCOVA models will be the baseline value of the continuous endpoint. Sensitivity analyses include use of non-parametric and influence-reducing regression for continuous endpoints (lowess plots and robust regression) and generalized linear models with scale factor estimation to account for under- or over-dispersion for binary endpoint data (dispersion-corrected logistic regression) and count endpoint data (dispersion-corrected negative binomial regression). Each secondary endpoint in the planned table of 16 secondary endpoints will be compared across the 3 vitamin E doses vs Placebo using treatment effect estimates, 95% confidence limits, and p-values. The Benjamini-Hochberg Method will be use to adjust the presented p-values for the false discovery rate (FDR) from the 16x3=48 pairwise p-values.

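### The secondary endpoint on change in adverse event frequency has no defined baseline, does not fit its planned Poisson model, and takes no account of time at risk

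*Combined protocol and SAP*

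**What the plan says.** The endpoint appears in the same words in the Section 3 table and in Section 9.1: "Change in frequency of CTCAE defined adverse events from baseline to 24 weeks". In Section 9.1 it is the twelfth of 16 secondary endpoints, all under the hypothesis that one or more doses do better than placebo.

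The text on what might serve as a baseline is scattered:

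- **Schedule (Section 1.3).** The row "Review for adverse effects" is blank at screening and at randomization and is first marked at week 4.
- **Randomization visit (Section 8.1.3).** "The procedures completed at the randomization visit are: verification that the patient is feeling well; affirmation of consent; review of concomitant drugs and vital signs". No adverse event review is named.
- **Recording (Section 8.3.4).** "Site coordinators will record all reportable events with start dates occurring any time after informed consent is obtained". It adds: "At each study visit, the investigator will inquire about the occurrence of AE/SAEs since the last visit".
- **Pre-existing conditions (Section 8.3.4).** "Any medical condition that is present at the time that the participant is screened will be considered as baseline and not reported as an AE".

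For analysis, Section 9.4.3 assigns "ANCOVA for continuous endpoints, logistic regression for binary endpoints, and Poisson regression for counts". It names a baseline covariate only for continuous endpoints and gives no exposure term for counts. It uses randomized participants with complete data on the endpoint when less than 10% are missing, and multiple imputation otherwise. Section 9.3 defines a Safety Analysis Dataset, but Section 9.4.3 does not use it for this endpoint.

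**The concern.** A change from baseline needs a baseline measurement. For ALT, glucose or weight there is one. For adverse events the plan does not say what it is: zero at randomization, the events recorded between consent and randomization, or something else. Two analysts following the plan could therefore build different variables from the same data, which a pre-specified endpoint should not allow.

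Each available reading has a difficulty. If screening events are subtracted, a variable window of at most about 60 days is set against 24 weeks, and the result can be negative. If nothing is subtracted, the endpoint is a raw count that treats someone followed for 8 weeks like someone followed for 24.

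The comparison matters because Section 2.3.3 justifies the search for a lower dose partly by the hope of avoiding long-term adverse effects. A 24-week count speaks only indirectly to long-term harm, but it is still the secondary endpoint that compares adverse events across doses.

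**Working it through.** **1. The plan's own figure.** Section 9.1 lists 16 secondary endpoints; with three doses against placebo, 16 × 3 = 48 p-values, as Section 9.4.3 states. This endpoint supplies 1 × 3 = 3 of them. Without it the family would be 15 × 3 = 45.

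**2. Length of the two periods.** Treatment lasts 24 × 7 = 168 days. The screening phase is 60 days (Sections 1.1 and 8.1.1), and the time from consent to randomization varies by participant. The ratio is at least 168 / 60 = 2.8.

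**3. Reading A: subtract the consent-to-randomization count.** The documents give no adverse event rate, so the following are assumptions: a constant rate λ of 0.5 to 3 events per 24 weeks, a screening window *b* of 7 to 60 days, and independent Poisson counts in the two periods. Let X be the screening count, with mean λ*b*/168, and Y the 24-week count, with mean λ. Then, with no true change in rate:

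- Mean change: E(Y − X) = λ(1 − *b*/168).
- Variance relative to Y alone: (λ + λ*b*/168)/λ = 1 + *b*/168. This is 1 + 7/168 = 1.04 at 7 days and 1 + 60/168 = 1.36 at 60 days.
- P(Y < X), from the distribution of the difference of two Poisson counts (Skellam).

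| λ per 24 weeks | Mean change, 7 days | P(negative), 7 days | Mean change, 60 days | P(negative), 60 days |
|---|---|---|---|---|
| 0.5 | 0.479 | 1.3% | 0.321 | 10.4% |
| 1 | 0.958 | 1.5% | 0.643 | 13.0% |
| 2 | 1.917 | 1.2% | 1.286 | 12.4% |
| 3 | 2.875 | 0.7% | 1.929 | 10.3% |

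So between 0.7% and 13% of participants would have a value that Poisson regression cannot take. The positive mean change reflects unequal periods only and is the same in expectation in every arm. The cost to the between-arm comparison is therefore variance (4% to 36%) and not bias. If a participant's two counts are positively correlated, the added variance would be smaller.

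**4. Reading B: baseline is the moment of randomization.** The baseline count is then zero by definition and the change equals the count from randomization to week 24. Poisson regression fits that, but no time at risk enters. As an illustration at λ = 3, a participant who leaves the study at week 8 expects 3 × 8/24 = 1 event, and one followed to week 24 expects 3, at the same underlying rate.

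**5. Missing-data rule under Reading B.** Section 7.2 lets an investigator withdraw a participant because of an adverse event. Section 9.4.3 does not say what complete data means for an event count. If it means 24 weeks of follow-up, such a participant's observed events are discarded in a complete-case analysis, or the count is imputed. An offset would keep those events with the time over which they were seen.

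**The case against.** The strongest reply is that Section 9.4.3 already shows what was meant. None of the other 15 endpoints is evidently a count, so Poisson regression, and negative binomial regression as its sensitivity analysis, have no other clear target. On that view the phrase simply means events occurring between baseline and week 24. This is probably the intent, and it removes the problem of negative values. It does not settle the definition: the text says change, as the neighbouring endpoints on glucose, anthropometrics and symptom scores do, and those are true change scores. Nor does it supply time at risk or a rule for early withdrawals.

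A reader might infer that the trial has no pre-randomization adverse event data, so that the endpoint cannot be computed at all. The documents do not support that. Section 8.3.4 records events from consent and has the investigator ask at each study visit; the blank schedule cells conflict with this and do not prove that nobody asks. A reader might also infer that the 2.8-fold difference in period length distorts the dose comparison. It does not: the screening window precedes assignment, so it affects all arms alike in expectation.

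Some further points in the plan's favour stand. Participants who stop study drug remain in follow-up (Sections 7.1 and 7.2), which limits differences in time at risk. The randomized and safety populations should differ little, because drug is issued at the randomization visit. Placing a safety outcome among the secondary endpoints is deliberate, as Section 3 says. Section 9.4.4 separately tabulates any event, the number of events per patient (0, 1, 2, 3 or more) and highest severity by arm, with Fisher's exact tests and no baseline subtraction.

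**Conclusion.** The point holds as a defect of definition. The endpoint as worded has no stated baseline and does not match its own analysis model; on the more likely reading as a plain count, it still has no time at risk and no clear rule for participants who leave early.

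Its reach is limited to one of 16 secondary endpoints, 3 of the 48 p-values in the false discovery rate family. The primary endpoint, the power and the Section 9.4.4 tables are unaffected. The 4% to 36% variance figure and the 0.7% to 13% chance of a negative value apply only if screening events are subtracted, and rest on the assumed rates, window lengths and independence. The size of the time-at-risk problem cannot be given, because it depends on how many participants withdraw before week 24. The documents do not support a claim of biased dose comparisons or of a trial without safety analysis. The correction is worth making before unmasking because it is cheap and removes a choice that would otherwise be made with the data in hand.

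**What to change.** 1. In Sections 3 and 9.1, define the endpoint as the number of CTCAE adverse events with onset from randomization to week 24, with no baseline subtraction. Randomization is the right anchor: Section 8.1.3 makes it time zero, Section 9.4.4 displays time since randomization, and the documents do not mention a recorded first-dose date.
2. In Section 9.4.3 (or 9.4.4), compare each dose with placebo on the Safety Analysis Dataset by Poisson or negative binomial regression, with log time at risk as offset. Time at risk runs from randomization to the earlier of the week 24 cut-off and last contact. State that the observed events of participants who withdraw are kept, and that the complete-case and imputation rule does not apply to this endpoint.
3. Decide where it is reported. If it moves to Section 9.4.4 as a safety outcome, change the false discovery rate family from 16 × 3 = 48 to 15 × 3 = 45. If it stays a secondary endpoint, the family remains 48.
4. Reconcile the schedule in Section 1.3, which marks no adverse event review before week 4, with Section 8.3.4, which records events from consent and asks about them at each visit.

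The cost is a few sentences. Onset times, randomization dates and follow-up are already collected. If the endpoint moves, the secondary table loses one row.

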9.2 SAMPLE SIZE DETERMINATION

The primary endpoint is the relative change in ALT at week 24 from baseline [i.e., (ALT at baseline – ALT at week 24)/ALT at baseline]. There are three vitamin E treatment groups: 133.4 mg/day, 266.8 mg/day, 533.6 mg/day and one placebo group. The primary analysis is intention-to-treat analysis of minimum effective dose using Williams' test of mean 24-week relative change in ALT. If the percentage of patients with missing follow-up data on the primary endpoint is greater than 10%, multiple imputation using chained equations method with 50 imputations modeling will be used to impute missing values; otherwise complete-case analysis will be used.

Among patients in PIVENS with baseline ALT ≥ 60 U/L, the mean 24-week relative change in ALT was 40% in the vitamin E (800 IU/day) group and 20% in the Placebo group. The Mean (SD) of the vitamin E – placebo difference in relative change (%) was -20% (31%). Using this estimate as the clinically meaningful difference, the trial has 90% power to detect a significant minimum effective dose given a sample size of 200 patients (50 per group with equal allocation) given a 2-sided Type I error of 5%, missing data rate of 10% and using Williams' test for minimum effective dose (MED) (Williams 1971, Williams 1972) obtained from PASS 2019 software (PASS 2019 Power Analysis and Sample Size Software (2019). NCSS, LLC. Kaysville, Utah, USA, ncss.com/software/pass).

The testing for minimum effective dose starts by comparing the 24-week relative change in ALT in each of the 3 dose groups with the placebo group using critical values obtained from Williams' test for MED. (Critical values will be obtained using SAS PROBMCM function.) Williams' test assumes the same or increasing efficacy with increasing dose; therefore, if the mean change at a dose level is less in absolute value than the mean change in a lower adjacent dose category, the groups are combined for statistical comparison. The lowest dose that is significantly different from placebo is declared the MED. By definition, all doses greater than the MED are also significantly different from placebo.

Sample size estimates for varying sizes of the treatment effect are given below given the same assumptions as above.

24-week relative change in ALT			Sample size	
Vitamin E	Placebo	Vitamin E – Plbo	No. / group	Total
48%	20%	28%	25	100
44%	20%	24%	34	136
40%	20%	20%	50	200
36%	20%	16%	76	304

32%	20%	12%	135	540
28%	20%	8%	303	1212

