- Any other condition which, in the opinion of the investigator, would impede compliance or hinder completion of the study, including inability to swallow treatment capsules
- Failure or inability to give informed consent

Sample size / Power:

- Total sample size = 200; 50 per group
- Power = 90%
- Type I error (2-sided) = 5%
- Increase in sample size due to missing data = 10%
- Mean (SD) difference (Vitamin E – Placebo) in relative change [(BL-FU)/BL] in ALT at 24 weeks = 20% (31%)
 - Mean relative change (%) in ALT at 24 weeks in placebo = 20% (based on data from PIVENS trial)
 - Mean relative change (%) in ALT at 24 weeks in Vitamin E = 40% (based on data from PIVENS trial)
- Method of analysis = Williams' test for minimum effective dose

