9.4 STATISTICAL ANALYSES

9.4.1 GENERAL APPROACH

The primary intention-to-treat analysis uses Williams' ANOVA-based test to find, with high statistical power (90%), the minimum effective dose of vitamin E that improves the per-person primary endpoint, defined as the percentage relative change in ALT from baseline over 24 weeks of treatment with either vitamin E or matching placebo. The sample size justification allows for 10% missing data using a complete-case Williams' test on the non-missing data; however, if the percentage of patients with missing data on the primary endpoint is greater than 10%, multiple imputation modeling at each step in the Williams' test procedure will be used to include all randomized patients in the determination of the step-by-step p-values needed for the Williams' test dose-finding procedure.

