9.4.2 ANALYSIS OF THE PRIMARY EFFICACY ENDPOINT(S)

- Intention-to-Treat (ITT) Analysis Dataset

The primary endpoint is 24-week relative change in serum ALT, defined as the ALT obtained at the 24-week visit minus ALT at the baseline visit divided by ALT at baseline [i.e., $(\text{ALT at baseline} - \text{ALT at week 24}) / \text{ALT at baseline}$]. The change in serum ALT is measured on a continuous scale and is a single endpoint. The Williams' ANOVA-based test for minimum effective dose of vitamin E starts by comparing the primary endpoint between the lowest vitamin E dose of 133.4 mg (200IU) vs. placebo. If significantly better ($p < 0.05$) using the 5th percentile from the Williams' test, then 133.4 mg is declared the minimum effective dose and no other comparisons are made; If the previous step is not significantly better, then the 266.8 mg (400 IU) dose is compared vs placebo. If significantly better ($p < 0.05$) using the 5th percentile from of the Williams' test, then 266.8 mg (400IU) is declared the minimum effective dose and no other comparisons are made. If the previous step is not significantly better, the 533.6 (800IU) mg dose is compared vs placebo. If significantly better ($p < 0.05$) using the 5th percentile from the Williams' test, the 533.6 (800IU) mg is declared the minimum effective dose and no other comparisons are made. If the previous step is not significantly better, then declare that no minimum effective dose for vitamin E was found. The primary analysis will present the (up to) 3 p-values from the Williams' test steps above and, only if the William's

test finds a minimum effective dose, the primary analysis will also include the estimated difference and 95% confidence interval for 24-week percentage relative change vs. baseline, comparing the minimum effective 24-week dose group vs placebo. As sensitivity analyses, the 3 separate comparisons of each vitamin E dose group vs placebo with estimates and 95% confidence limits be presented. Sensitivity analyses will include use of robust regression to down-weight the effect on the Williams' test minimum effective dose selection of influential outliers in the relative ALT change from baseline measures. Other sensitivity analyses may be used to balance potential effects on results of confounders not balanced out by randomization, as judged by the trial Data Safety and Monitoring Board.

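### Sections 1.1 and 9.2 label the primary test 2-sided 5%, but the sample-size table, and apparently the decision rule in 9.4.2, use a one-sided 5% Williams' test

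*Combined protocol and SAP*

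**What the plan says.** The sample-size block of the synopsis (1.1) gives "Type I error (2-sided) = 5" percent, power of 90%, a 20-point difference with SD 31%, and "Increase in sample size due to missing data = 10" percent. Section 9.2 claims the same 90% power for 50 in each of the four arms, by Williams' test. The error rate and the allowance for missing data enter there as "given a 2-sided Type I error of 5%, missing data rate of 10" percent. It then tabulates 25, 34, 50, 76, 135 and 303 per group for differences of 28, 24, 20, 16, 12 and 8 points, on what it says are the same assumptions.

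Section 9.4.2 sets out the decision rule. Each dose, starting from the lowest, is tested for being significantly better than placebo at p<0.05, using the 5th percentile from the Williams' test. If an MED is found, "the primary analysis will also include the estimated difference and 95% confidence interval for 24-week percentage relative change vs. baseline" for that dose against placebo. Section 9.4.1 describes the test as finding, "with high statistical power (90%), the minimum effective dose of vitamin E".

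**The concern.** A 2-sided 5% test leaves 2.5% in the direction of benefit. A test for being better, at a 5% point, puts the whole 5% there. The two descriptions imply different critical values, and therefore different power at the same sample size. A reader of 1.1 or 9.2 would take an MED claim to carry a 2.5% error rate in the benefit direction when the rule in 9.4.2 appears to allow 5%. The 95% interval reported beside the decision belongs to the 2-sided reading, so it can include zero for a dose declared effective.

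**Working it through.** **Inputs.** Difference 20 points, SD 31, 90% power, 50 per group, 10% missing (1.1 and 9.2). Section 9.4.1 plans complete-case analysis at that level of missing data, so 45 per group are evaluable and the error df are 4 × 44 = 176. Section 9.2 describes the 31% as the SD of the treatment difference. It is used here as the common per-patient SD, the reading that reproduces the table.

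**Critical values.** Williams' test with three doses and 176 df, by simulation: about 1.75 with 5% in the benefit tail and about 2.05 with 2.5% (1.74 and 2.03 at infinite df).

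**Reproducing the table.** Evaluable n per group = 2 × 31² × (c + 1.2816)² / difference². The last two columns multiply this by 1.1 for missing data.

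| Difference | Printed | Evaluable n, c = 1.75 | × 1.1, c = 1.75 | × 1.1, c = 2.05 |
|---|---|---|---|---|
| 28 | 25 | 22.5 | 24.8 | 29.9 |
| 24 | 34 | 30.7 | 33.7 | 40.7 |
| 20 | 50 | 44.2 | 48.6 | 58.7 |
| 16 | 76 | 69.0 | 75.9 | 91.7 |
| 12 | 135 | 122.7 | 134.9 | 163.0 |
| 8 | 303 | 276.0 | 303.6 | 366.7 |

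One-sided 5% fits all six rows to within rounding. In the main row, 44.2 rounds up to 45 evaluable, and 45 × 1.1 = 49.5, or 45 / 0.9 = 50. In the last row the df are large, so c is nearer 1.74; that gives 274.2 × 1.1 = 301.6, and the printed 303 lies between the two results. Two-sided 5% fits no row.

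**Power at 50 randomised, 45 evaluable per group.** SE = 31 × √(2/45) = 6.54, and 20 / 6.54 = 3.06.
- One-sided 5%: Φ(3.06 − 1.75) = Φ(1.31) = 90.5%.
- Two-sided 5%: Φ(3.06 − 2.05) = Φ(1.01) = 84.4%.

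Simulation with pooling of out-of-order doses gives the same two figures when only 800 IU has the 20-point effect. At 2-sided 5%, the simulated chance of declaring some MED depends on the true effects at 200, 400 and 800 IU:

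| True effects (points) | Chance of declaring some MED |
|---|---|
| 0, 0, 20 | 84% |
| 5, 10, 20 | 85% |
| 6.7, 13.3, 20 | 86% |
| 10, 15, 20 | 87% |
| 0, 20, 20 | 91% |
| 20, 20, 20 | 93% |

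**Sample size for 90% at 2-sided 5%, top dose only.** With c = 2.05, n = 53.3, so 54 evaluable: 54 × 1.1 = 59.4 and 54 / 0.9 = 60. That is 59 to 60 per group.

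**Interval against decision.** Suppose the observed differences are 11, 12 and 13 points at 200, 400 and 800 IU. No pooling is needed, and t = 1.68, 1.84 and 1.99. All exceed the one-sided 5% Williams values of 1.65, 1.73 and 1.75, so 200 IU is the MED. An ordinary unadjusted 95% interval for it is 11 ± 1.97 × 6.54, or −1.9 to 23.9.

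**The case against.** The strongest reply is that the design is coherent and only a label is wrong. Section 9.2 itself says Williams' test assumes the same or increasing efficacy with dose, the rule in 9.4.2 is directional, and the table matches that rule. On this reading the trial has its 90%, and 2-sided in 1.1 and 9.2 is a slip. This stands. A reader might infer that actual power is 84%, or that the trial is about ten patients per group short. The documents do not support that: the 84% arises only if the test is changed to fit the label, and then only when the top dose alone works. Section 9.2 states no dose-response shape.

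The headline 50, taken alone, is also close to a plain 2-sided two-sample formula with no missing-data allowance (51), which fits the first three rows too. But it gives 79, 141 and 316 for the last three rows, and it ignores both Williams' test and the 10% allowance. Only the whole table identifies the one-sided value. The software output is not in the documents, so its alpha convention and rounding cannot be checked.

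Two further inferences go too far. The interval conflict follows from the same sidedness question and is not a second error; section 9.4.2 also does not say how the interval is built. And the wording of 9.4.1 may suggest a 90% chance of naming the right dose. Simulated correct selection at one-sided 5% is 84% to 89% when each dose has either no effect or the full 20 points. Reporting such figures would be useful, but their absence is not an arithmetic fault.

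**Conclusion.** The inconsistency is real and concerns the primary decision rule. The stated 2-sided 5% level, with the stated Williams' test, 10% missing data and 90% power, does not give 50 per group or any other row of the table; a one-sided 5% level gives all of them. Under the rule as 9.4.2 reads, power is about 90.5% and the label is wrong. Under the label, power is about 84% for an effect at the top dose alone, and 85% to 93% to declare some MED for the other shapes examined. These figures rest on a common SD of 31, 45 evaluable per group, a 20-point maximum effect, and reading the 5th percentile as a single 5% tail. The documents do not show which level was intended, so the text must settle it. They do not establish that the trial is underpowered.

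**What to change.** Make 1.1, 9.2 and 9.4.2 state one sidedness, by either route:

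- **(a) One-sided 5%.** Relabel the test in 1.1 and 9.2, keep the table and 50 per group, and report a 90% two-sided interval or a one-sided 95% bound for the declared MED.
- **(b) Two-sided 5%.** Keep the label, specify upper 2.5% Williams critical values in 9.4.2 alongside the 95% interval, restate power as about 84% (effect at the top dose only, 10% missing), and recompute the table.

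Under either route, say in 9.2 and 9.4.1 which dose-response shape the stated power refers to. Settle this before unmasking. The cost is wording, plus recomputing the table under (b), and no extra patients. The price is an openly one-sided test under (a), or a less favourable stated power under (b).
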